- x. Adverse events will be collected from the time of signing the informed consent form, throughout the treatment period, and including the follow-up period.
- y. Other systemic NF1-PN targeted treatments will be collected for all participants who discontinue selumetinib until the time when they would have completed 25 cycles of treatment, or they commence an alternative systemic NF1-PN treatment whichever is the earliest.
- z. Consent can be performed on Day -42 onwards. All screening assessments must be performed within 28 days prior to dosing.

CCI	; BSA, body surface area; C, cycle; CSP, Clinical Study Protocol;
D, day; CCI	; ECG, electrocardiogram; EDC, electronic data capture; EoT, end of treatment; CC
CCI	; FU, follow-up; CCI
CCI	LLN, lower limit of normal; LVEF, left ventricular ejection fraction; MRI, magnetic resonance imaging; NF1, neurofibromatosis
type 1; PD, pharmacodynamic	: CC : PK, pharmacokinetic(s): PN, plexiform neurofibroma: SoC, standard of care;

VMI, Visual-Motor Integration; W, week.

AstraZeneca

	Participants receiving selumetinib treatment a			Participants no longer receiving selumetinib treatment		
Procedure b	Every 6 cycles	Every 12 cycles	EoT Safety Follow-up (30 days after last dose)	Every 6 months	Every year	Section or Appendix
Window	±7 days	±7 days	+ 7 days	± 7 days	±7 days	
Full Physical examination	Х		X	Х		8.3.1
Height, weight	Х		X	Х		8.3.2
BSA	Х			Х		8.3.2
Clinical safety laboratory assessments	Х		X	Х		8.3.9
12-lead ECG	Х		Х	If clinically	y indicated	8.3.4
Echocardiogram	Approximately	every 3 cycles	Х	If clinically indicated		8.3.5
Ophthalmology examination		X	Х	If clinically	y indicated	8.3.6
Knee MRI/X-ray (Physeal dysplasia)		X			Х	8.3.7
Performance status	Х		Х	Х		8.3.8
Urinalysis	Х		Х	Х		8.3.9
Vital signs	Х		Х	Х		8.3.3
CI	1	1				
Dispense medication d	To be dispensed	l every 2 cycles				6
Return Medication/Compliance Check		>	Х			6.2 6.4
SAEs and AEs causally related to selumetinib	←======	→	Х	← =======	→	8.4

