Participants who are aged  $\geq$  5 years at the end of 25 cycles of selumetinib will be considered to have completed the study for data analysis purposes. Participants who terminate treatment prior to Cycle 25 will be followed up to collect MRIs performed as standard of care, and details of NF1-PN treatment information until the time when they would have completed 25 cycles of treatment, or they commence an alternative systemic NF1-PN treatment, whichever is the earliest. Any participant who is aged < 5 years after 25 cycles of selumetinib (or when they terminate treatment with selumetinib) will enter a safety follow-up phase until they reach the age of 5 years or commence an alternative systemic NF1-PN treatment, whichever is the earlier. Participants can continue to receive selumetinib (capsule or granule formulations) during the safety follow-up as long as they are considered to be receiving benefit in the opinion of their Investigator. The safety follow-up is designed to assess long term safety of selumetinib treatment in participants who are < 3 CONFIDENTIAL AND PROPRIETARY 40 of 168 Clinical Study Protocol -5.0 Astra Selumetinib - D1346C00004 years of age when they commence selumetinib as there are no long term safety data currently available for patients who received selumetinib at this age.

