# 8.4.1 Time Period and Frequency for Collecting AE and SAE Information

Adverse events will be collected from the time of signature of the ICF until 30 days after the last dose of selumetinib or 25 cycles of treatment, whichever is earlier. For participants taking part in the long term safety follow-up (participants < 5 years of age), after 25 cycles of treatment or end of treatment, adverse events causally related to selumetinib will be collected until they complete the study in accordance with Table 3. No AEs will be collected for participants who are > 5 years of age who remain in the study after 25 cycles of treatment.

SAEs will be collected from time of signing the ICF throughout a subject's participation in the study.

If the Investigator becomes aware of an SAE with a suspected causal relationship to the IMP that occurs after the end of the clinical study in a participant treated by him or her, the Investigator shall, without undue delay, report the SAE to the Sponsor.

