### 8.4.13 Adverse Events of Special Interest

Adverse events of special interest are events of scientific and medical interest specific to the further understanding of the selumetinib safety profile and require close monitoring and rapid communication by the investigators to AstraZeneca. An AESI can be serious or non-serious. All AESI should be recorded in the eCRF as soon as possible, and preferably within 24 hours of occurrence. Serious AESIs will be recorded and reported as per Section 8.4.9. Adverse events of special interest based on examinations and tests should be reported in accordance with Section 8.4.5.

Adverse events of special interest are shown in Table 14.

AESI	MedDRA Preferred Terms Defining the AESIs	
Ocular toxicity	Chorioretinopathy (central serous retinopathy [CSR]); Retinal detachment; Retinal tear; Vision blurred; Visual impairment; Vitreous floaters; Photopsia; Eye disorder; Photophobia; Retinal vein occlusion (RVO); Detachment of retinal pigment epithelium (Retinal pigment epithelial detachment [RPED]).	
Hepatotoxicity	Drug-induced liver injury; ALT increased; AST increased.	
Muscular toxicity	Blood creatine phosphokinase increased; Musculoskeletal pain; Muscular weakness; Myalgia; Rhabdomyolysis; Myoglobin blood increased; Myoglobin urine present; Acute kidney injury; Myopathy.	
Cardiac toxicity	Ejection fraction decreased; Oedema peripheral; Peripheral swelling; Oedema; Left ventricular dysfunction; Ventricular dysfunction.	
Physeal dysplasia	Metaphyseal dysplasia; Multiple epiphyseal dysplasia; Arthralgia; Joint stiffness; Joint hyperextension; Gait disturbance; Short stature.	
Choking on the capsule	Choking; Retching.	

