4.6.2 Adverse Events

4.6.2.1 Definitions and Derivations

The MedDRA version 26.1 or higher is used to code AEs. AEs are graded according to the CTCAE version 5.0.

AEs will be collected from the time of signature of the ICF until 30 days after the last dose of selumetinib or 25 cycles of treatment, whichever is earlier. For participants taking part in the long-term safety follow-up (participants < 5 years of age), after 25 cycles of treatment or end of treatment, AEs causally related to selumetinib will be collected until they complete the study in accordance with CSP Table 3. The long-term safety follow-up is designed to assess the long-term safety of selumetinib treatment in participants who are < 3 years of age when they commence selumetinib, as there are no long-term safety data currently available for patients who received selumetinib at this age. No AEs will be collected for participants who are > 5 years of age who remain in the study after 25 cycles of treatment.

A treatment-emergent AE will be defined as an AE that starts, or worsens, after the first dose of selumetinib up to and including 30 days after the last dose of selumetinib.

AEs of special interest

Some clinical concepts (including some selected individual preferred terms and higher-level terms) have been considered AESIs to the selumetinib program.

The AESIs in [Table 16](#) have been identified as a list of categories by the patient safety team.

Table 16 **AEs of special interest**

AESI	MedDRA Preferred Terms Defining the AESIs
Ocular toxicity	Chorioretinopathy (central serous retinopathy [CSR]); Retinal detachment; Retinal tear; Vision blurred; Visual impairment; Vitreous floaters; Photopsia; Eye disorder; Photophobia; Retinal vein occlusion (RVO); Detachment of retinal pigment epithelium (Retinal pigment epithelial detachment [RPED]).
Hepatotoxicity	Drug-induced liver injury; ALT increased; AST increased.
Muscular toxicity	Blood creatine phosphokinase increased; Musculoskeletal pain; Muscular weakness; Myalgia; Rhabdomyolysis; Myoglobin blood increased; Myoglobin urine present; Acute kidney injury; Myopathy.
Cardiac toxicity	Ejection fraction decreased; Oedema peripheral; Peripheral swelling; Oedema; Left ventricular dysfunction; Ventricular dysfunction.
Physeal dysplasia	Metaphyseal dysplasia; Multiple epiphyseal dysplasia; Arthralgia; Joint stiffness; Joint hyperextension; Gait disturbance; Short stature.
Choking on the capsule	Choking; Retching.

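### Non-serious AESIs judged unrelated to drug must be recorded under protocol 8.4.13 but are not collected in the long-term follow-up under 8.4.1, Table 3 and SAP 4.6.2.1

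*Protocol*

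**What the plan says.** Protocol 8.4.13 sets the AESI rule. "An AESI can be serious or non-serious", and "All AESI should be recorded in the eCRF as soon as possible, and preferably within 24 hours of occurrence". It attaches no causality condition and no end date. For findings from examinations and tests it adds one qualification: "Adverse events of special interest based on examinations and tests should be reported in accordance with Section 8.4.5".

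Protocol 8.4.1 sets the collection periods. All-causality collection stops at the earlier of two points: "Adverse events will be collected from the time of signature of the ICF until 30 days after the last dose of selumetinib or 25 cycles". For children under 5 who then enter the long-term safety follow-up, "after 25 cycles of treatment or end of treatment, adverse events causally related to selumetinib will be collected until they complete the study". SAEs are collected throughout participation, whatever their cause. The corresponding row of Table 3 in section 1.3 reads "SAEs and AEs causally related to selumetinib". SAP 4.6.2.1 repeats the rule: "AEs causally related to selumetinib will be collected until they complete the study in accordance with CSP Table 3". None of these three places exempts AESIs.

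Protocol 4.1.2 gives the purpose of the phase: "The safety follow-up is designed to assess long term safety of selumetinib treatment in participants who are" under 3 years old when they start, a group for whom it says no long-term safety data exist. Children may stay on selumetinib during this phase if the investigator sees benefit.

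**The concern.** Read together, the sections give a site two different instructions for the same event. A two-year-old who has finished 25 cycles and then develops non-serious arthralgia that the investigator considers unrelated has an AESI that 8.4.13 wants in the eCRF, but there is no collection rule for it in 8.4.1 or Table 3. Some sites may record it and others may not.

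Two things are at stake. First, this is the phase meant to supply the missing long-term safety data, and the trial has no control arm. Filtering events by individual attribution before they reach the database removes information that cannot be restored by analysis. Second, SAP 4.6.2.2 tabulates AESIs without a relatedness condition, although it provides separate related versions for several other categories. For a child still on drug after cycle 25, the treatment-emergent window in SAP 4.6.2.1 stays open. The same AESI count would then join all-causality capture up to cycle 25 with related-only capture of non-serious events afterwards.

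**Working it through.** **Which events are in conflict.** The plan gives no figure to reproduce here, so the first check sets the rules side by side for the follow-up phase.

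| AESI in long-term follow-up | 8.4.13 | 8.4.1, Table 3, SAP 4.6.2.1 |
|---|---|---|
| Serious, related | record | collected |
| Serious, unrelated | record | collected |
| Non-serious, related | record | collected |
| Non-serious, unrelated | record | not collected |

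Only the last row conflicts. It narrows further because other rules apply throughout the study. Section 8.4.5 restricts which test deteriorations become AEs and excludes physical findings unequivocally due to the disease. Sections 8.4.7 and 8.4.8 keep out events unequivocally due to progression or to NF1-PN itself, with exceptions in 8.4.8 for events that are serious or lead to discontinuation. What remains is non-serious events that are not plainly disease but that the investigator still judges unrelated.

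**Which AESI terms depend on AE reporting.** Table 3 continues several assessments regardless of causality:

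- On and off drug: physical examination, height and weight, laboratory tests (CK, ALT and AST are in Table 13), vital signs, performance status and knee imaging.
- On drug as scheduled, off drug only if clinically indicated: ECG, echocardiogram and eye examination.

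Growth, growth-plate, CK and transaminase findings are therefore measured directly. Symptom terms in Table 14, such as arthralgia, myalgia and blurred vision, have little support outside the AE record. Off drug, the cardiac and eye terms also have less support.

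**How much time falls under the restricted rule.** Inputs: 25 cycles of 28 days, and follow-up to age 5. Assumption: all 25 cycles are completed on schedule.

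- Treatment period: 25 × 28 = 700 days; 700 / 365.25 = 1.916 years.
- Share of time from first dose to age 5, for starting age a: (5 − a − 1.916) / (5 − a).
- a = 1.0: 2.084 / 4.0 = 52%.
- a = 2.0: 1.084 / 3.0 = 36%.
- a = 2.9: 0.184 / 2.1 = 9%.

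Stopping drug early while under 5 starts the restricted period sooner. Starting another systemic NF1-PN treatment ends the follow-up.

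**Where the two capture rules meet.** SAP 4.6 presents off-treatment follow-up data separately in the tables, so the mixture within one count arises for children who stay on drug past cycle 25. The off-treatment tables are separate, but their non-serious AESIs are also filtered by causality.

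**The case against.** The best counter-argument is that the sections can be reconciled as they stand. Section 8.4.1 is headed as the section on collection periods, while 8.4.13 concerns how quickly AESIs are entered. AESIs are a subset of AEs, so 8.4.13 could mean that AESIs falling inside the 8.4.1 window are recorded promptly. An unlimited 8.4.13 would also override the statement in 8.4.1 that no AEs are collected from children over 5 who remain after 25 cycles. The related-only rule appears in three places and looks deliberate.

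That reading is possible, but 8.4.13 does not state it, and footnote x to Table 2, which says AEs are collected through the follow-up period, adds to the ambiguity. Even if it is right, the follow-up AESI counts still carry a causality filter that SAP 4.6.2.2 does not mention.

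Other parts of the objection stand and limit the point. All SAEs are collected. Events unequivocally due to NF1-PN are excluded anyway, so the change would not recover them. Safety analysis is descriptive, and no comparison of AESI rates with external data is planned.

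A reader might infer that late growth, eye and muscle toxicity will go undetected, or that investigators will usually answer no on causality. The documents do not support either. Height, weight, CK and knee imaging continue on and off drug. The causality guide in Appendix B 3 points both ways: it asks about underlying disease as an alternative cause, and also about consistency with the known drug profile, on which AESI terms would tend to score.

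**Conclusion.** The inconsistency is real and confined to one group: non-serious AESIs in the long-term follow-up that are judged unrelated and not already excluded as unequivocally due to NF1-PN. The likely result is omission or uneven recording between sites, mainly for symptom-based terms. AESI counts for children on drug past cycle 25 would also mix two capture rules.

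The restricted rule covers between about 9% and 52% of the time to age 5 for starting ages from 2.9 down to 1.0, if 25 cycles are completed. That is a share of time, not a measure of bias. A reader might be tempted to turn it into an under-count, for example by taking a true AESI incidence of 20% and an attribution fraction of 30% to 80% to get a recorded 6% to 16%. Neither input is in the documents, and the multiplication treats every AESI as non-serious although serious ones are always collected. The size of any under-count cannot be derived from the plan.

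**What to change.** Reconcile protocol 8.4.1, 8.4.13, Table 3 and SAP 4.6.2.1. State that Table 14 AESIs are collected regardless of investigator causality throughout the long-term safety follow-up, on and off drug, subject to the existing rules in 8.4.5, 8.4.7 and 8.4.8. Keep causality as a recorded attribute. In the SAP, show all AESIs and related AESIs side by side for the follow-up, separately from the period up to cycle 25.

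The cost is wording in both documents, a few extra AE entries at visits that already take place, and a somewhat higher reported AESI rate. No new procedure is needed. Because uncollected events may not be recoverable at the final data cut-off, the change is best made before children enter the follow-up.

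If the sponsor prefers to keep the related-only rule, 8.4.13 must say that its requirement is limited in this way. The AESI tables must then report the two capture periods separately and label the follow-up counts as SAEs plus related events only. This alternative needs no extra data but leaves the causality filter in place.

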#### 8.3.5 **Echocardiogram**

An ECHO to assess LVEF will be performed at the visits as shown in the SoA. Participants should be examined using the same machine and operator whenever possible, and quantitative measurements should be taken (i.e., accurate to 1% and not estimated to 5%).

Left ventricular ejection fraction, end diastolic, and end systolic left ventricular volumes should be recorded at each ECHO assessment.

Participants experiencing an asymptomatic LVEF reduction or left ventricular systolic dysfunction should be managed according to the algorithm provided in Appendix E 1.

Participants who have a drop in LVEF of  $\geq 10$  percentage points from baseline and to below the LLN at the time of selumetinib discontinuation should, where possible, have follow-up ECHO, ECG, vital signs and weight performed after 30 days to evaluate the potential for reversibility.

An ECHO will also be carried out if a participant develops signs and/or symptoms suggestive of deterioration in left ventricular function/cardiac event.

A further ECHO should be performed as part of the assessment package for any cardiorespiratory AE with no obvious diagnosis (obvious causes will be managed in accordance with local clinical practice) and additionally at the discretion of the Investigator if clinically indicated.

If a participant has had an ECHO performed within 4 weeks prior to treatment discontinuation, the discontinuation visit ECHO scan is not required unless clinically indicated.

Concomitant cardiac symptoms should be reported as AEs/SAEs accordingly. Cardiac failure should be treated and followed according to local medical practice.

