#### 8.4.5 Adverse Events Based on Examinations and Tests

The results from the CSP mandated laboratory tests, vital signs, physical examinations, ECGs, ECHO scans and ophthalmological examinations will be summarised in the Clinical Study Report.

Deterioration as compared to baseline in CSP-mandated laboratory tests, vital signs, ECGs, echocardiogram scans and ophthalmological examinations should therefore only be reported as AEs if they fulfil any of the SAE criteria, are the reason for discontinuation of treatment with the investigational product or are considered to be clinically relevant as judged by the Investigator (which may include but not limited to consideration as to whether treatment or non-planned visits were required or other action was taken with the study intervention, eg, dose adjustment or drug interruption).

If deterioration in a laboratory value/vital sign/ECG/ECHO is associated with clinical signs and symptoms, the sign or symptom will be reported as an AE and the associated laboratory result/vital sign/ECG/ECHO will be considered as additional information. Wherever possible the reporting Investigator uses the clinical, rather than the laboratory term (eg, anaemia versus low haemoglobin value). In the absence of clinical signs or symptoms, clinically relevant deteriorations in non-mandated parameters should be reported as AE(s).

Deterioration of a laboratory value, which is unequivocally due to disease progression, should not be reported as an AE/SAE.

Any new or aggravated clinically relevant abnormal medical finding at a physical examination as compared with the baseline assessment will be reported as an AE unless unequivocally related to the disease under study.

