#### D 4.2 Potential Hy's Law Criteria met

If the participant does meet PHL criteria the Investigator will:

- Notify the AstraZeneca representative who will then inform the central Study Team
- Within one day of PHL criteria being met, the Investigator will report the case as an SAE of PHL; serious criteria 'Important medical event' and causality assessment 'yes/related' according to CSP process for SAE reporting.
- For participants that met PHL criteria prior to starting IMP, the Investigator is not required to ٠ submit a PHL SAE unless there is a significant change# in the participant's condition.
- The Medical Monitor contacts the Investigator, to provide guidance, discuss and agree an • approach for the study participants' follow-up (including any further laboratory testing) and the continuous review of data.
- Subsequent to this contact the Investigator will:
- Monitor the participant until liver biochemistry parameters and appropriate clinical symptoms and signs return to normal or baseline levels, or as long as medically indicated. Completes follow-up SAE Form as required.
- Investigate the aetiology of the event and perform diagnostic investigations as discussed with the Medical Monitor.
- Complete the three Liver eCRF Modules as information becomes available.

**\*A 'significant' change** in the participant's condition refers to a clinically relevant change in any of the individual liver biochemistry parameters (ALT, AST or TBL) in isolation or in combination, or a clinically relevant change in associated symptoms. The determination of whether there has been a significant change will be at the discretion of the Investigator, this may be in consultation with the Medical Monitor if there is any uncertainty.

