### D 5 Review and Assessment of Potential Hy's Law Cases

The instructions in this section should be followed for all cases where PHL criteria are met.

As soon as possible after the biochemistry abnormality was initially detected, the Medical Monitor contacts the Investigator in order to review available data and agree on whether there is an alternative explanation for meeting PHL criteria other than DILI caused by the IMP, to ensure timely analysis and reporting to health authorities within 15 calendar days from date PHL criteria was met. The AstraZeneca Global Clinical Lead or equivalent and Global Safety Physician will also be involved in this review together with other subject matter experts as appropriate.

According to the outcome of the review and assessment, the Investigator will follow the instructions below.

Where there is an agreed alternative explanation for the ALT or AST and TBL elevations, a determination of whether the alternative explanation is an AE will be made and subsequently whether the AE meets the criteria for a SAE:

- If the alternative explanation is **not** an AE, record the alternative explanation on the appropriate eCRF.
- If the alternative explanation is an AE/SAE: update the previously submitted PHL SAE and AE eCRFs accordingly with the new information (reassessing event term; causality and seriousness criteria) following the AstraZeneca standard processes.

If it is agreed that there is **no** explanation that would explain the ALT or AST and TBL elevations other than the IMP:

- Send updated SAE (report term 'Hy's Law') according to AstraZeneca standard processes.
  - The 'Medically Important' serious criterion should be used if no other serious criteria apply.

- As there is no alternative explanation for the HL case, a causality assessment of 'related' should be assigned.

If there is an unavoidable delay of over 15 calendar days in obtaining the information necessary to assess whether or not the case meets the criteria for HL, then it is assumed that there is no alternative explanation until such time as an informed decision can be made:

- Provides any further update to the previously submitted SAE of PHL (report term now 'Hy's Law case') ensuring causality assessment is related to IMP and seriousness criteria is medically important, according to CSP process for SAE reporting.

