4.6.2.2 Presentation

Summary tables of the number and percentage of participants with AEs by system organ class and preferred term will be produced for below categories. The number and percentage of participants with AESIs will be summarised by AESI grouped term and preferred term. An overall summary table will include the number and percentage of participants in each category.

- All AEs
- AEs possibly related to study intervention
- AEs of CTCAE grade 3 or higher
- AEs with CTCAE grade 3 or higher, possibly related to study intervention
- SAEs with an outcome of death
- SAEs with outcome of death possibly related to intervention
- All SAEs
- SAEs possibly related to study intervention
- AEs leading to discontinuation of study intervention
- AEs leading to discontinuation of study intervention, possibly related to study intervention
- AEs leading to dose interruption and reduction (separately)
- AESIs
- OAEs

The number of subjects and events will also be presented for non-serious AEs occurring in more than 5% of participants.

CTCAE grades and summaries of the number and percentage of participants will be provided by system organ class, preferred term and maximum reported CTCAE grade.

All AEs, SAEs, AESIs, AEs with outcome of death, AEs leading to treatment discontinuation, and AEs occurring > 30 days after last dose of selumetinib will be listed in the same subject listing.

All AEs listings will include the formulation (granule or capsule) variable at the event start date of the event.

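### The liver and cardiac AESI term lists can leave cardiac failure, jaundice and possibly Hy's Law cases out of the AESI summary

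*Protocol*

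**What the plan says.** AESIs belong to the primary safety endpoint. Protocol Section 3 (Table 5) names them among the AE assessments, and the endpoint table in SAP Section 4.2 classes them as primary.

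Protocol Section 8.4.13, Table 14, defines six AESI categories by MedDRA preferred terms. Hepatotoxicity has three: "Drug-induced liver injury; ALT increased; AST increased". Cardiac toxicity has six: "Ejection fraction decreased; Oedema peripheral; Peripheral swelling; Oedema; Left ventricular dysfunction; Ventricular dysfunction". SAP Section 4.6.2.1, Table 16, repeats both lists. Its lead-in reads "Some clinical concepts (including some selected individual preferred terms and higher-level terms) have been considered AESIs to the selumetinib program", but the table holds preferred terms only, so no broader search is specified. SAP Section 4.6.2.2 then states: "The number and percentage of participants with AESIs will be summarised by AESI grouped term and preferred term".

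Four protocol rules bear on which term reaches those lists:

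- Section 8.4.13 sends test-based AESIs to Section 8.4.5. There, when a laboratory, vital-sign, ECG or ECHO deterioration comes with signs or symptoms, the sign or symptom becomes the AE and the test result is supporting detail. It adds: "Wherever possible the reporting Investigator uses the clinical, rather than the laboratory term".
- Section 8.4.4 prefers a diagnosis to a string of symptoms.
- Appendix D covers combined transaminase and bilirubin elevation. Once the criteria are met, "the Investigator will report the case as an SAE of PHL" (D 4.2). If no cause other than the study drug is agreed, the instruction is "Send updated SAE (report term 'Hy's Law') according to AstraZeneca standard processes" (D 5).
- Section 8.3.5 foresees heart failure only as a matter of care: "Cardiac failure should be treated and followed according to local medical practice". It has cardiac symptoms reported as AEs or SAEs but prescribes no report term.

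**The concern.** Membership of the list decides whether a child is counted. The muscular list runs from raised creatine phosphokinase to rhabdomyolysis and acute kidney injury, and the ocular list reaches retinal vein occlusion and retinal detachment. The liver and heart lists have no organ-failure term, and the liver list has no bilirubin or jaundice term. The reporting rule meanwhile moves an event away from a listed test term once symptoms appear. In these two categories a missed count is therefore more likely for the symptomatic presentation than for the asymptomatic one.

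The AESI table is the study's focused summary of the recognised selumetinib risks. A reader who sees no hepatotoxicity or cardiac toxicity there would take that as reassurance, although a case might sit elsewhere in the report under another term.

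**Working it through.** No figure in the plan needs reproducing. The check compares the terms sites are told or allowed to use with the terms that are counted, and then sizes one missed case.

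**1. Term match.** Liver: 0 of the 3 listed terms is a PHL or Hy's Law term, and 0 of 3 is a bilirubin, jaundice or hepatic failure term. One of 3, drug-induced liver injury, is the concept through which Appendix D 1 defines Hy's Law. Heart: 0 of 6 is a cardiac failure term, 2 of 6 are ventricular dysfunction terms, 3 of 6 are oedema or swelling, and 1 of 6 is the ejection fraction test term (2 + 3 + 1 = 6).

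**2. Tracing a case through the rules.**

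| How the event is recorded | Counted as AESI? |
|---|---|
| Isolated ALT or AST rise, judged clinically relevant | Yes |
| ALT rise recorded only as jaundice | No |
| SAE reported as PHL or Hy's Law | Only if coded to drug-induced liver injury, or if a listed enzyme term is also reported |
| Asymptomatic LVEF fall, judged clinically relevant | Yes |
| Symptomatic LVEF fall recorded as ventricular dysfunction or with oedema | Yes |
| Symptomatic LVEF fall recorded only as cardiac failure or dyspnoea | No |

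The PHL and Hy's Law row stays conditional because those are report terms. They are MedDRA coded before matching (Protocol Section 9.4.3.1, SAP Section 4.6.2.1), and neither document gives the mapping.

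**3. Size of one missed case.** The number treated is redacted, so assume n between 20 and 40.

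- One case: 1/40 = 2.5% to 1/20 = 5.0%.
- At n = 30, the AESI table would show 0/30 instead of 1/30 = 3.3%.
- The exact two-sided 95% upper limit for 0/n is 1 − 0.025^(1/n). For n = 30 it is 11.6%, for n = 20 it is 16.8% and for n = 40 it is 8.8%. For 1/30 the exact upper limit is 17.2%.

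The SAP plans no confidence limits for AESIs. They are given only to show how far the reading of the table would shift.

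**The case against.** Several points against this are sound.

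- **Hy's Law.** A reader might infer that a Hy's Law case is certainly left out of the hepatotoxicity count. The documents do not support that. Appendix D 1 makes the absence of any explanation other than drug-induced liver injury from the study drug the test for Hy's Law, and that injury is a listed term. The intent to capture these cases is plausible; what is missing is a rule that secures it, above all for a PHL report still under review.
- **Heart.** A reader might infer that the protocol tells sites to use an uncounted term for cardiac failure. It prescribes none. The LVEF guidance in Section 8.3.5 and Appendix E 1 speaks of left ventricular systolic dysfunction, and ventricular dysfunction and oedema are listed, so some symptomatic cases would count. Section 8.4.5 also lets a test deterioration be an AE when it is serious or leads to discontinuation.
- **Physeal dysplasia.** It is tempting to extend the criticism there, but dysplasia, short stature, arthralgia and gait terms are listed, and knee or wrist imaging has its own frequency table (SAP Section 4.6.10.2).
- **Visibility.** The events also enter the all-AE and SAE tables, and PHL, which must be reported as related, enters the related-event tables. ALT, AST, bilirubin and ejection fraction have CTCAE shift tables, and PHL has a listing (SAP Sections 4.6.2.2, 4.6.3.2 and 4.6.8.2). In a small single-arm study such a case would be seen.
- **Laboratory rule.** Counting every laboratory PHL case would include some later explained by another cause.

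These points limit the concern to one output and make the Hy's Law part conditional. They do not remove the two rows in the table where the event is plainly not counted. The last point is met by a flag, since the listed enzyme terms are themselves counted whatever the cause.

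**Conclusion.** The point holds in a limited form. As written, the counting rule can understate the more severe presentation in two AESI categories that belong to the primary safety endpoint. A symptomatic LVEF fall recorded only as cardiac failure or dyspnoea, or an ALT rise recorded only as jaundice, is not counted. A PHL or Hy's Law report may or may not be, depending on coding that neither document states.

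The effect is confined to the AESI summary. The magnitude above rests on three assumptions: the treated number lies between 20 and 40, such a case occurs, and no listed term is recorded alongside it. It is worth correcting because the correction is cheap, not because safety information would be lost from the report.

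**What to change.** Before the next database lock, amend Protocol Table 14 and SAP Table 16 together:

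1. Add cardiac failure terms to cardiac toxicity.
2. Add hepatic failure, jaundice and bilirubin-increased terms to hepatotoxicity.
3. State that events reported as PHL or Hy's Law count as hepatotoxicity, whatever preferred term they are coded to.
4. Also count as hepatotoxicity, regardless of cause, any participant who meets the laboratory PHL rule in SAP Section 4.6.3.2 (ALT or AST ≥ 3 × ULN and total bilirubin ≥ 2 × ULN, transaminase rise first or on the same day). Flag those later given an alternative explanation.

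The patient safety team should confirm the exact preferred terms.

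The cost is a wording change in two tables and a small change to the term search; the laboratory rule is already specified. The AESI rate may come out slightly higher, and the list will differ slightly from the programme-level one, which a footnote can explain.
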